5.3.2. Exclusion Criteria

Potential participants meeting any of the following criteria will be excluded from enrollment.

1. Receipt of any investigational HIV vaccine or investigational adjuvant
2. Received an investigational product or vaccine in the 30 days before enrollment. This does not include products with emergency use authorization.
3. Concurrent participation in another clinical research study
4. Any serious medical illness or condition

5. Receipt of immunoglobulins or blood products within 3 months before enrollment
6. Any history of anaphylaxis or allergy to study product
7. History of sickle cell trait or disease
8. Pregnancy, lactation, or intention to become pregnant during the study
9. History of active/recent cancer still within treatment or active surveillance follow-up (except basal cell carcinoma of the skin and cervical carcinoma in situ). Treated/resolved cancers with no likelihood of recurrence may be deemed acceptable at PI discretion
10. History of autoimmune disease
11. History of PIMMCs
12. Suspected or known current alcohol or drug abuse as defined by an alcohol intake of greater than 3 drinks a day on average for a man, and greater than 2 drinks a day on average for a woman
13. Any other significant disease, disorder or finding which may significantly increase the risk to the participant because of participation in the study, affect the ability of the participant to give informed consent, participate in the study, or impair interpretation of the study data, in the opinion of the Investigator
14. History of splenectomy
15. History of confirmed or suspected immunodeficiency
16. History of Hereditary angioedema (HAE) acquired angioedema (AAE), or idiopathic forms of angioedema
17. History of asthma that is unstable or required emergent care, urgent care, hospitalization, or intubation during the past 2 years
18. History of diabetes mellitus (type I or II), with the exception of gestational diabetes
19. History of thyroid disease (except for well controlled hypothyroidism)
20. History of idiopathic urticaria within the past year
21. History of hypertension that is not well controlled by medication or that is persistently greater than 140/95 at screening
22. History of bleeding disorder diagnosed by a doctor (e.g., factor deficiency, coagulopathy, or platelet disorder requiring special precautions) or significant bruising or bleeding difficulties with IM injections or blood draws
23. History of chronic or active neurologic disease to include seizure disorder and chronic migraine headaches. Exceptions are: i) childhood febrile seizures, or ii) seizures secondary to alcohol withdrawal more than 3 years ago
24. Participants receiving any of the following substances

- a. Systemic immunosuppressive medications or cytotoxic medications within 12 weeks before enrollment [with the exception of a short course of corticosteroids (\leq 14 days duration or a single injection) for a self-limited condition at least 2 weeks before enrollment; inhaled, intranasal or topical steroids are not considered exclusionary]
- b. Treatment with known immunomodulators including allergy immunotherapy (other than NSAIDs) for any reason
- c. Live attenuated vaccines within 30 days before initial study vaccine administration
- d. Medically indicated subunit, mRNA, or killed vaccines, e.g., influenza, pneumococcal, vaccines with QS-21 as an adjuvant, or allergy treatment with antigen injections, planned for administration 14 days before or after study vaccine administration

25. History of arthritis diagnosis other than osteoarthritis

26. History of other diagnosed rheumatoid disorders

27. Has an acute illness or temperature \geq 38.0 °C/100.4 °F on any study injection day or within 48 hours of planned study injection.

28. Note: Participants will not be excluded from further consideration for enrollment and study injections. Volunteers with fever or an acute illness on the day of study injection or in the 2 days before the study injection may be re-assessed by a study physician for resolution of the condition and enrolled and receive the study injection so long as the injection is within allowable windows. Military personnel will be excluded from participation in this study, regardless of leave status due to the potential for a false-positive HIV test result on mandatory HIV testing. This could have adverse effects on deployment status.

Final evaluation of eligibility will be based on the medical judgment of the investigator based on his/her medical and research experience.

5.4. Lifestyle and Reproduction Restrictions

Only restrictions to contraception and pregnancy are required.

5.4.1. Contraception and Pregnancy

Risks to unborn babies and nursing infants are unknown at this time. Therefore, participants childbearing potential must agree to follow contraceptive guidance and must agree not to breastfeed while in the study and for 2 months after the study.

5.4.1.1. Individuals of Childbearing Potential

Participants are not considered of childbearing potential if they meet any of the following criteria:

- Premenopausal with 1 of the following:
 - Documented hysterectomy

- Documented bilateral salpingectomy
- Documented bilateral oophorectomy
- Premenarchal
- Postmenopausal
- Defined as no menses for 12 months without an alternative medical cause (A high follicle stimulating hormone (FSH) level in the postmenopausal range may be used to confirm a postmenopausal state in women not using hormonal contraception or hormonal replacement therapy (HRT). However, in the absence of 12 months of amenorrhea, a single FSH measurement is insufficient.)
- People assigned female sex at birth on HRT and whose menopausal status is in doubt will be required to use one of the nonhormonal highly effective contraception methods if they wish to continue their HRT during the study, or they must discontinue HRT to allow confirmation of postmenopausal status before protocol enrollment

5.4.1.2. Participants of Childbearing Potential

Participants of reproductive potential are eligible to participate if they agree to use a highly effective method of contraception as described the section below.

5.4.1.3. Effective Methods of Contraception

Highly effective contraceptive methods that have a failure rate of <1% per year when used consistently and correctly:

- User Dependent Methods:
 - Oral, intravaginal, or transdermal combined (estrogen- and progestogen- containing) hormonal contraception associated with inhibition of ovulation
 - Oral or injectable progestogen-only hormonal contraception associated with inhibition of ovulation
- User Independent Methods:
 - Implantable progestogen-only hormonal contraception associated with inhibition of ovulation
 - Intrauterine device (IUD)
 - Intrauterine hormone-releasing system (IUS)
 - Bilateral tubal occlusion

- Vasectomized partner
- Sexual abstinence

5.4.1.4. Pregnancy Testing

Participants of childbearing potential will be included in the study only after a negative pregnancy test. Additional pregnancy testing will be performed according to [Table 1](#) Schedule of Evaluations and whenever a menstrual cycle is missed or when pregnancy is otherwise suspected.

6. STUDY INTERVENTION

6.1. Treatments Administered

All products to be administered in this study are described in [Table 4](#). Investigational product is defined as any investigational treatment or a product/device being used for an indication that has not been approved/cleared by the U.S. Food and Drug Administration (FDA).

Table 4: Products Administered

	Investigational Product	Investigational Product	Investigational Product
Compound	A244	B.63521	ALFQ
Dosage formulation:	0.5 mg/mL of the A244 gp120 protein, 20 mM Tris, 123 mM NaCl pH 7.4	0.60 mg/mL of the B.63521gp120 protein, 20 mM sodium phosphate, 150 mM NaCl, 0.02% polysorbate 80(PS80), pH 6.5.	The concentration of DMPC is 25.8+/-3.9 mM. The concentration of DMPG 2.9 +/- 0.4 mM. The synthetic cholesterol concentration is 34.9+/1 5.2mM
Unit dose strength(s)/dosage level(s):	300 ug	300 ug	Arm 1 will contain 200ug MPLA/3D-PHAD®, Arm 2 will contain 100 ug MPLA/3D-PHAD®, and Arm 3 will contain 50ug MPLA/3D-PHAD®. ALFQ also contains 100ug of QS-21.
Route of administration:	IM	IM	IM
Manufacturer:	Vetter Development Services USA Inc. For: NIH/NIAID	Vetter Skokie, IL for NIH/HIAID	Walter Reed Pilot Bioproduction Facility

6.2. Preparation, Handling, Storage, and Accountability

6.2.1. Acquisition Accountability

The sponsor's representative is responsible for distributing the investigational product to the study site and has ultimate responsibility for product accountability.

Responsibility for investigational product (IP) accountability at the trial site rests with the investigator/institution.

The sponsor's representative may release the product to other clinical study sites.

After the investigational product is distributed, the site pharmacy personnel are responsible for maintaining logs of investigational product receipt, storage, reconstitution, accountability by subject, and remaining before final disposition within the site. The investigational product should be stored as specified by the sponsor. The PI may delegate, in writing, this responsibility to another individual, but the PI is ultimately responsible for the investigational product and its proper storage upon receipt at the study site until it is transferred back to the sponsor's representative, or designee, or is destroyed, as directed by the sponsor's representative.

The empty vials and the unused portion of the vial should be discarded in a biohazard containment bag and incinerated after verification from the monitor. Any unopened vials (past the re-test date or otherwise) that remain will be destroyed at the discretion of the sponsor in accordance with local site SOP as directed by the Sponsor's representative and as stipulated by local, state, and Federal regulations. Partially used vials or expired prepared doses will not be administered to other participants or used for *in vitro* experimental studies. They will be disposed of in accordance with institutional pharmacy policy. Retest dates shall be updated as per analytical analyses of the IP. No IP shall be administered to a participant beyond the current retest date. The decision for final disposition of the investigational product rests with the sponsor.

Any temperature excursions during product storage must be reported to the sponsor and the affected IP must be placed in quarantine status. The sponsor will determine the disposition on the affected product.

Further guidance and information for the final disposition of unused study treatment are provided in the pharmacy section of the Manual of Operations (MOP).

6.2.2. Product Storage and Stability

All study products will be transported in accordance with the labeled storage conditions.

Once at the study site, all study products will be stored in a secure, environmentally controlled, and monitored (manual or automated) area in accordance with the labeled storage conditions with access limited to the investigator and authorized site staff. Only participants enrolled in the protocol may receive study injections, and only authorized site staff may supply or administer study injections.

The investigator or designee will confirm that appropriate temperature conditions have been maintained during transit for all study products received and that any discrepancies are reported and resolved before use of the study products.

6.2.3. Product Preparation

All investigational product preparation will be performed by the unblinded study nurse on the day of vaccine administration, after confirmation by the clinical staff that the participant is present, is eligible for enrollment into the study, and has received their randomization assignment. The unblinded study nurse will perform all manipulations of investigational products in accordance with GCP guidelines. The unblinded study nurse will wear a lab coat and gloves for all manipulations. The center seals of the vials will be removed and the vial stoppers wiped with an alcohol wipe prior to insertion of a sterile needle attached to a sterile syringe. The Pharmacy section of the MOP outlines specific product preparations.

6.3. Study Intervention Compliance

All IP is administered by the study team and documented on the Study Vaccine Administration CRF. A study vaccination outside of a participant's vaccination window may occur at the discretion of the PSRT.

6.4. Measures to Minimize Bias: Randomization and Blinding

The PI, study staff, and participants will be blinded as to group allocation as it pertains to the dose of ALFQ. Since the vaccines are not identical in appearance, to preserve blinding the material inside the syringe will be masked. In addition, the delegated un-blinded study staff/nurse preparing the vaccine syringes will not be involved in the clinical assessment of participants and will be instructed not to comment on the appearance of experimental agent to study staff. For all participants, the volume of injection will be consistent.

Delegated un-blinded study staff/nurse staff will be trained in GCP and instructed not to discuss the vaccine randomization lists, codes, or participant assignments with study personnel. Unblinded study staff will be the only person(s) on site who will know the randomization assignment. The randomization assignment will not appear on any label or source document. Samples will be labeled on site using labels containing participant study numbers, protocol number and visit number. The samples will be accompanied by a specimen tracking form that records the study number, date and time of sample collection.

Any request for unblinding, with its rationale, must be forwarded through the PI. The PI will evaluate the request and will notify the Protocol Chair/Sponsor's Medical Expert for the Trial and HIV Vaccine Product Manager. They will evaluate the request and will advise the United States Army Medical Research and Development Command (USAMRDC) Office of Regulated Activities (ORA) Product Safety Surveillance Office (PSSO) regarding a course of action. A PVG physician from the USAMRDC ORA PSSO will decide whether to approve the request for unblinding.

In the case of a decision to unblind, the Sponsor will authorize the independent statistician to provide this information to the PI, who must notify the WRAIR IRB (see [Table 7](#)) and provide the study assignment to the site physician. It should be noted that there are very few circumstances in which unblinding will be essential to the medical management of a vaccine recipient. The site investigator will report episodes of accidental unblinding, with an explanation, to Protocol Chair/Sponsor's Medical Expert for the Trial, the Institution Review Boards (IRBs)

and the USAMRDC ORA PSSO. Follow-up of unblinded participants will continue through the duration of the trial.

After completion of the study and database lock, the Sponsor will authorize the independent statistician to prepare a list containing each participant's unblinded treatment assignment.

Participants will be contacted to return to clinic or will be notified via phone or letter ([Appendix A](#)) of their unblinded treatment assignment.

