APPENDIX B. ROLES AND RESPONSIBILITIES

- Principal Investigator
 - Supervises sub investigators and protocol nurse coordinator
 - Is responsible for completing informed consent process
 - Trains study staff
 - Screens individuals and reviews all of the screening tests to determine eligibility of an individual to participate in the study
 - Makes the final participant eligibility decisions or appoints a qualified designee
 - Permits auditing by the site quality unit, the US Army MRDC Quality Unit, and the ORA Quality and Compliance Office
 - Assures adequate resources, time, and participant population to meet study requirements
 - Provides medical care for AEs
 - Documents protocol deviations
 - Reports all SAEs to (WRAIR IRB, MRDC) and sponsor's safety office (US Army Medical Research and Development Command) Product Safety Surveillance Office (PSSO), WRAIR IRB
 - Delegates investigational product accountability and administration
 - May reconstitute vaccine
 - May administer investigational product to study participants
 - Evaluates AEs for diagnosis, relationship, and severity
 - Ensures documentation and safety reporting
- Sub-investigator
 - Assists the PI in conduct of the study and may include (as indicated on the Delegation of Responsibilities Log) the following duties:
 - Is responsible for completing informed consent process
 - Assists in supervising study staff
 - Reviews all of the screening tests to determine eligibility of an individual to participate in the study

- Screens individuals for protocol participation (physical examination and medical history)
- Can make final eligibility decisions
- May reconstitute vaccine as designated by the PI
- May administer investigational product to study participants
- Evaluates AEs
- If designated by the PI, to assist the PI in protocol adherence and execution, management and reporting, and any other duties described under PI responsibilities
- Protocol Nurse/Study Coordinator
 - May be responsible for investigational vaccine accountability
 - May be responsible for completing informed consent process
 - Reviews all of the screening tests to determine eligibility of an individual to participate in the study
 - May reconstitute vaccine as designated by the PI
 - May administer investigational product to study participants
 - Schedules follow-up appointments
 - Follows up on all moderate and SAEs
 - Coordinates all study activity to include all participant visits and any non-compliant participants

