### 4.5.4. Blinding

The PI, study staff, and participants will be blinded as to group allocation as it pertains to the dose of ALFQ. The unblinded pharmacy team will maintain all of the accountability logs and other product related regulatory documents, such as completed preparatory sheets. These documents will not be accessible to the blinded team. The unblinded pharmacy team will be in charge of emergency access to unblinding. In addition, the delegated unblinded study staff/nurse preparing the vaccine syringes will not be involved in the clinical assessment of participants and will be instructed not to comment on the appearance of experimental agent to study staff. For all participants, the volume of injection will be consistent. Procedures used for drug packaging and distribution to maintain blinding are described in the pharmacy manual and the clinical manual of procedures. To prevent a blinded person from seeing the IP in the syringe, the unblinded nurses will use blinding tape to prevent blinded study staff from looking at the viscosity and color of the product while in the syringe.

In a non-emergency event when a unexpected serious adverse reaction occurs that is suspected (i.e. possible/probably related) to the treatment, the study PI or designee will send an unblinding request to [rv575\\[contact]](mailto:[contact]), with ORA PSSO safety mailbox in copy, that includes the participant ID, reason for unblinding, and who should receive the unblinding information. The unblinded team at DCAC will provide the treatment assignment to the ORA PSSO representative within one business day of the request. Additional details are provided in the blinding management plan.

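### Protocol 6.4 and SAP 4.5.4 give incompatible unblinding routes, and the protocol's route tells the otherwise blinded PI, who grades AE severity and relationship, the released participant's dose

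*Protocol*

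**What the plan says.** Protocol section 6.4 begins by stating who is blinded: "The PI, study staff, and participants will be blinded as to group allocation as it pertains to the dose of ALFQ". It then describes a single route with no split between emergency and non-emergency requests: "Any request for unblinding, with its rationale, must be forwarded through the PI". The PI brings in the Protocol Chair/Sponsor's Medical Expert and the product manager, who advise the sponsor safety office (ORA PSSO). There, "A PVG physician from the USAMRDC ORA PSSO will decide whether to approve the request for unblinding". If approved, "In the case of a decision to unblind, the Sponsor will authorize the independent statistician to provide this information to the PI"; the PI must then notify the IRB and "provide the study assignment to the site physician". The same section keeps unblinded participants in follow-up to the end of the trial.

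SAP section 4.5.4 has two routes. For emergencies, "The unblinded pharmacy team will be in charge of emergency access to unblinding". For a non-emergency, unexpected serious reaction suspected to be due to treatment, the PI or designee sends a request with the safety office mailbox in copy. The request gives the participant, the reason and the intended recipient of the information. Then "The unblinded team at DCAC will provide the treatment assignment to the ORA PSSO representative within one business day of the request". For further detail the SAP points to a blinding management plan, which is not among the documents.

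On assessment, the PI's duties in protocol Appendix B include: "Evaluates AEs for diagnosis, relationship, and severity". Protocol section 8.2.4 has the investigator assess severity and relationship for all AEs. Protocol Table 3 makes both part of a primary endpoint for unsolicited AEs.

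**The concern.** A site facing a suspected unexpected serious reaction has two governing texts that disagree on who approves, who releases and who is told. Whichever it follows, it departs from the other.

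The choice of recipient matters for the analysis. SAP section 7.1.2 tabulates unsolicited AEs by severity and by relationship as the investigator judged it, and SAP Table 7 carries p-values across the three ALFQ doses. If the PI knows one participant's dose, later judgements on that participant are no longer blinded. The PI or designee is also needed for a PSRT meeting (protocol section 7.2.1), and the pause criteria in section 8.2.11.3 depend on relatedness and grade. Neither document requires grades to be recorded before release, names a blinded assessor afterwards, or marks assessments made after release.

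**Working it through.** No alpha, power or sample-size figure is involved, so the check sets the texts side by side and then traces what remains open to bias.

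**1. The case both documents cover: a non-emergency, suspected, unexpected serious reaction**

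| Step | Protocol 6.4 | SAP 4.5.4 |
|---|---|---|
| Approver | PVG physician in the safety office | None stated |
| Releaser | Independent statistician | Unblinded DCAC team |
| Recipient | PI, then site physician | Safety office representative, plus an open field in which the requester names recipients |
| Time limit | None stated | One business day from the request |

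Approver, releaser and recipient all differ. In the public copy the address that receives the SAP request is removed, so only the releaser is certain, not the first recipient of the request.

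**2. Emergencies.** The protocol's single chain applies to any request. The SAP puts the pharmacy team in charge. These also disagree.

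**3. Does the protocol's route reach an endpoint assessor?** Yes. Section 6.4 names the PI as recipient, and Appendix B and section 8.2.4 make the PI or investigator the grader. The site physician, who is told next, may also be the physician assigning causality under section 8.2.8.

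**4. What is left to bias once a release has happened?**
- *Triggering event.* The SAP route opens only when the reaction is already suspected. Protocol Tables 8 and 9 call for an SAE report within 24 hours of awareness, with severity and relationship among its contents. The first grade therefore normally precedes release, though no rule says that it must, and regrading stays possible.
- *Reactions to later doses.* Protocol section 7.2 ends vaccination after an SAE believed to be related, so this participant contributes none.
- *Later unsolicited AEs, SAEs and AESIs.* These are still collected and graded.

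**5. Size.** Each arm has 20 participants, so one whose classification changes moves an arm's proportion by 1/20 = 5 percentage points (1/60 = 1.7% of the trial). That participant already counts in the row of SAP Table 7 for any related unexpected event because of the trigger. Only regrading the trigger could remove them from it. Later events would mainly affect the severity and relationship entries by preferred term in SAP Table 11.

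**The case against.** The strongest reply is that little is exposed. Protocol section 6.4 expects very few cases in which unblinding is essential to care. The trigger is usually graded first, and the independent safety monitor gives a separate relationship opinion within 24 hours (section 8.2.9). Every arm receives the same antigens with ALFQ, so a release reveals dose level and not active versus placebo. Severity follows the DAIDS table. Telling the PI after formal approval is a defensible choice, and the blinding management plan may settle the procedure. All of this limits the size. It does not remove the contradiction, because an unseen plan does not correct conflicting protocol text. Nor does it supply the missing safeguard for later grading.

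A second reply is that sending the code to the safety office only moves the problem. Appendix B gives that office the final say on SAE relatedness, and its PVG physician is a PSRT member. This stands: no route here blinds every causality assessor. What restricting the recipient protects is the investigator's determination, which is the one SAP section 7.1.2 tabulates.

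A third reply also stands. Simply deleting the PI from section 6.4 would remove the protocol's only stated path to the site physician. Any restriction must therefore be limited to non-emergency releases.

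**Conclusion.** The contradiction is established from the text: two incompatible routes for non-emergency releases and two for emergencies. Under the protocol's route, a blinded assessor of a primary endpoint learns the dose of the participant concerned. The effect is expected to be rare and applies to one participant at a time. It covers that participant's later unsolicited AEs, SAEs and AESIs and any regrading of the trigger. This rests on the SAE being judged related, so that vaccination stops, and on the 24-hour report being filed before release.

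Three stronger readings are tempting and are not supported.
- *The primary-endpoint assessor is unblinded across the trial.* A release concerns one participant, and the others stay masked.
- *The SAP already keeps the PI blinded.* It names a safety office representative but does not say that no one else is told, and the requester may name the PI.
- *The 4:1:1 sentinel split spreads any release to the other sentinel participants.* Before a release, each has a 4/6 = 67% chance of being in Arm 1. The likelier release, of an Arm 1 participant, moves the others down to 3/5 = 60%. An Arm 2 or Arm 3 release moves them up to 4/5 = 80%, and certainty needs both of those participants to be released. The shift is modest in the likeliest case, and the point does not depend on it.

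**What to change.** Reconcile protocol section 6.4 and SAP section 4.5.4, and the blinding management plan if needed, so that they name one approver, one releaser and one recipient, with emergency and non-emergency requests described separately.

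- **Non-emergency (regulatory) releases only.** Restrict the recipient to the sponsor safety office. Remove the PI as recipient, and remove the SAP field in which the requester names recipients. State that the safety office also determines SAE relatedness, so the judgement being protected is the investigator's.
- **Before any release.** Require the investigator's severity and relationship grades for the triggering event to be recorded.
- **After any release.** Have a sub-investigator who has not seen the code grade that participant's later AEs; Appendix B already gives that role AE evaluation. Alternatively, flag post-release assessments in the SAP listings.
- **Emergency access.** The two documents must be brought into agreement by the sponsor. No particular route is proposed here.

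The cost is wording in two sections, plus a flag in the listings if that option is chosen, using roles that already exist. The small downside is that a released case needs its later grading reassigned or flagged.
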